2.2. BACKGROUND

Trm cells can develop within tissues in response to certain pathogens.¹ They are long-lived and responsible for tissue protection from re-exposure to the original pathogen. When re-activated by re-exposure to that pathogen, Trm cells amplify immune responses by recruiting additional immune cells from blood. Interestingly, Trm cells are also found in skin previously affected by active psoriasis, vitiligo, and fixed drug reaction skin, and are now believed to be the cells responsible for recurrences of psoriasis.²⁻⁶ In psoriatic skin, these cells are CD8+CD103+ epidermal T cells that produce IL-17A.²⁻⁶ It is unknown whether psoriatic Trm cells are under the control of IL-23, but recently, guselkumab, an IL-23 blocker used to treat psoriasis, was shown to reduce Trm cells in skin after 6 months of dosing.⁷ Of note, similar IL-17A-producing cells (Th17 and Tc17 effector cells) in psoriasis are dependent upon IL-23 for survival.⁸

Many excellent treatments exist for the treatment of patients with moderate-to-severe plaque psoriasis. Disease, however, recurs following withdrawal of these treatments. risankizumab, an anti-IL-23 biologic, is highly effective and safe for treating plaque psoriasis.⁹⁻¹¹ The standard dose for this drug is 150 mg at Weeks 0 and 4, and then 150 mg every 12 weeks after two induction doses. Approximately 80% of patients reach PASI 90 and approximately 60% reach PASI 100 at 1 year, with few-to-no side effects.⁹⁻¹¹ In addition, the IMMhance study revealed that some patients undergoing risankizumab withdrawal demonstrated prolonged skin clearance long after their last dose; more specifically, 10-15% of patients with completely clear skin after only 3 risankizumab doses (at Weeks 0, 4, and 16) maintained completely clear skin for up to 1 year before psoriasis recurred.¹¹ The combination of these prior clinical results suggests there is a need to scientifically explore the biologic basis of the duration of risankizumab's therapeutic activity; specifically, there is a need to test higher doses at weeks 0, 4, and 16 to determine whether more complete skin clearance at one year can be achieved.

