4.4. END OF STUDY DEFINITION

Patients will be observed for 100 weeks after their first dose of risankizumab (84 weeks after their last dose of risankizumab).

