6.4. STUDY INTERVENTION COMPLIANCE

6.5. CONCOMITANT THERAPY

6.5.1. RESCUE MEDICINE

No rescue medications or concomitant therapies for psoriasis will be allowed in this study.

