8. STUDY ASSESSMENTS AND PROCEDURES

8.1. EFFICACY ASSESSMENTS

Clinical Assessments

All assessments will be performed at Oregon Medical Research Center, P.C. At screening, Week 0, Week 2, Week 4, and every visit thereafter until Week 100, the following will be done:

1. Physical examination (*complete exam at screening, baseline, Week 4, Week 16, and Week 52; targeted exam at every other visit per Investigator discretion)
2. Psoriasis Area and Severity (PASI)
3. Body Surface Area (BSA)
4. Static Physician's Global Assessment (sPGA)
5. DLQI (*at Weeks 0, 28, and 52 only)
6. Vital signs (temperature, blood pressure, heart rate, respiratory rate, and weight)
7. Past medical history, including past systemic treatments for psoriasis (*at screening visit only)
8. Columbia Suicide Severity Rating Scale (*at screening visit only)
9. Interim health history to assess for possible adverse events (*at all visits following the baseline visit)

Laboratory Assessments

At screening, Weeks 4, 8, 22, and 52, the following will be collected at Oregon Medical Research Center, P.C. and sent to a local laboratory:

1. Complete blood count (CBC) w/differential
2. Comprehensive metabolic panel
3. Urinalysis
4. Urine pregnancy test (*performed on-site only for women of child-bearing potential, at each visit up to Week 52, except Week 2)

At screening only, the following will be collected at Oregon Medical Research Center, P.C. and sent to a local laboratory:

1. HIV antibody
2. Hepatitis B panel
3. Hepatitis C antibody
4. Quantiferon Gold

At Weeks 0 and 52, the following will be collected at Oregon Medical Research Center, P.C. and shipped to the laboratory of [name] at the University of Michigan:

1. One 6 mm skin biopsy of lesional skin (at Weeks 0 and 52) and one 6 mm skin biopsy of peri-lesional skin (at Week 0); both will be bisected and processed as follows:

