9.4. HANDLING OF POTENTIAL INTERCURRENT EVENTS

There will be two major types of intercurrent events (ICE) in this study: risankizumab discontinuation due to lack of efficacy or intolerance, and risankizumab discontinuation due to other reasons. Each intercurrent event will be addressed by different strategies, specifically:

Table ** Handling of Potential Intercurrent Events

Intercurrent Event	Strategy	Description
risankizumab or study discontinuation due to lack of efficacy or intolerance	Composite variable strategy	Data after risankizumab or study discontinuation due to lack of efficacy or intolerance will be set to non-responder for binary endpoints. For continuous endpoints, set to last observation before discontinuation.
risankizumab discontinuation due to other reasons	Treatment policy strategy	Data after risankizumab discontinuation due to other reasons will be used regardless of whether the intercurrent event occurs.

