9.6. METHODS FOR ANALYSIS OF PRIMARY OUTCOMES

For the primary outcomes, after handling of intercurrent events as specified in Section 9.4, the change from baseline in the number and/or effector function of epidermal CD8+CD103+ Trm cells at Week 52 will be summarized with mean, standard deviation, 95% confidence interval, and compared between the two treatment arms with t-test. Additional analysis with non-parametric test (e.g., Wilcoxon signed-rank test) will be performed, as appropriate. Details will be provided in the SAP.

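### Section 9.6 compares change in Trm number between arms without baseline adjustment: a valid t-test, but it loses more than half the information if the Week 52 SD is below about 0.69 of the baseline SD

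*Combined protocol and SAP*

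**What the plan says.** Section 9.6 takes change from baseline to Week 52 in the number and/or effector function of epidermal CD8+CD103+ Trm cells, "after handling of intercurrent events as specified in Section 9.4". It states that this change "will be summarized with mean, standard deviation, 95% confidence interval, and compared between the two treatment arms with t-test". The only other analysis it names is a non-parametric test, also without a baseline term. It closes with "Details will be provided in the SAP"; no fuller SAP is in the text available. ANCOVA and LSMEANS are in the abbreviation list (Section 10.2), but no analysis section uses them.

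Section 8.1 schedules the tissue: "One 6 mm skin biopsy of lesional skin (at Weeks 0 and 52". Every patient with a Week 52 value should therefore already have a baseline lesional value. Section 9.2 sets the size at 20 on feasibility, and Section 4.1 randomizes 1:1, giving 10 per arm. Section 7.1 does not replace withdrawn patients. Section 9.4 treats discontinuation for lack of efficacy or intolerance as follows: "For continuous endpoints, set to last observation before discontinuation".

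**The concern.** A change score subtracts the whole baseline value. If treatment lowers Trm counts and their spread shrinks too, most of the variation in the change is baseline variation, and the arm comparison inherits it as noise. Regression on baseline removes only as much of the baseline value as predicts Week 52.

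The study is descriptive and unpowered (Sections 9.1 and 9.2), so how precisely it estimates the arm difference is most of what the primary analysis can offer. With the number of patients fixed by feasibility, the choice of analysis is one of the few ways left to improve that precision, and the covariate is already collected.

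The point covers Trm number only. Effector function has no defined metric to which the calculation could be applied.

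**Working it through.** **Inputs.** From the protocol: 20 patients, 10 per arm, t-test on change, lesional biopsies at Weeks 0 and 52. No SD, correlation or effect size is given, so there is no figure of the plan's to reproduce. Assumed over a range: k = SD(Week 52)/SD(baseline) and ρ = correlation of baseline with Week 52.

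**Bound.** With baseline SD set to 1:
- variance of change: 1 + k² − 2ρk
- ANCOVA residual variance: k²(1 − ρ²)
- correction for estimating the slope: 1 + 1/(N − 4), which is 1.0625 at N = 20
- variance ratio, ANCOVA to t-test: R = 1.0625 × k²(1 − ρ²)/(1 + k² − 2ρk)

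For k below 1, R is largest at ρ = k, where it equals 1.0625k². Setting 1.0625k² = 0.5 gives k = √(0.5/1.0625) = 0.686. Below that, R is under 0.5 for every correlation. With 16 evaluable the correction is 1 + 1/12 and the threshold √(0.5/1.0833) = 0.68; with 12 it is 1 + 1/8 and √(0.5/1.125) = 0.67. Because the bound uses only a ratio of SDs, it holds for a count, a density or a fraction.

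| k | Largest R, N = 20 | Smallest loss |
|---|---|---|
| 0.3 | 0.10 | 90% |
| 0.5 | 0.27 | 73% |
| 0.69 | about 0.50 | about half |
| 0.8 | 0.68 | 32% |

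At k = 1, R is 0.53 with ρ = 0 and 1.01 with ρ = 0.9. Bivariate-normal simulation with 10 per arm agrees: for k = 0.5, ρ = 0.5, simulated 0.268 against formula 0.266; for k = 0.8, ρ = 0.8, 0.679 against 0.680. At exactly k = 0.69 and ρ = 0.7 the formula gives 0.506, so the threshold is approximate.

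**Skewed counts, no dose effect.** Log-normal simulation, 10 per arm; baseline CV 0.3, 0.5 or 0.8; residual log-SD 0.5 to 1.0; log-log slope 0.3, 0.6 or 0.9; 36 settings per row:

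| Mean share of cells remaining | R | Settings losing more than half |
|---|---|---|
| 15% | 0.01–0.39 | 36 |
| 30% | 0.05–0.81 | 26 |
| 50% | 0.14–0.98 | 11 |
| 80% | 0.33–1.04 | 1 |
| 100% | 0.47–1.07 | 1 |

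That is 36 + 26 + 11 + 1 + 1 = 75 of 180 settings. Type I error is 3.2–5.6% for the t-test and 2.9–4.8% for ANCOVA.

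**Effect of Section 9.4.** Lesional biopsies exist only at Weeks 0 and 52, so a patient falling under the last-observation rule before Week 52 is carried at baseline with zero change. With the overall mean still 30% remaining and 20% of patients so carried (residual log-SD 0.5 or 0.7), R is 0.74–0.77 at CV 0.3, 0.50–0.54 at CV 0.5 and 0.30–0.34 at CV 0.8. More than half is then lost only at the highest CV.

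**Coverage when the arms differ.** Same log-normal settings, overall mean 30% remaining, nominal 95%:

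| Remaining, by arm | t-test on change | Raw-count ANCOVA |
|---|---|---|
| 25% vs 35% | 94–96% | 93–95% |
| 20% vs 40% | 94–96% | 88–94% |
| 15% vs 45% | 93–96% | 82–92% |

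Log-scale ANCOVA, for the ratio between arms, covers 94–96%.

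**Price of adjusting when it does not help.** At k = 1.2, ρ = 0.8, the ANCOVA interval is 3.2% wider on average with 10 per arm, and at least 13% wider in 5% of trials. With 6 per arm it is about 7% wider on average.

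**The case against.** The strongest objection is that the loss depends on a ratio nobody has. The only Trm reduction cited, in Section 2.2, is for a different IL-23 blocker, which "was shown to reduce Trm cells in skin after 6 months of dosing". Here follow-up ends "84 weeks after their last dose of risankizumab", which puts the last dose at Week 16 (100 − 84), so the Week 52 biopsy comes 36 weeks after it. Section 6.5.1 adds: "No rescue medications or concomitant therapies for psoriasis will be allowed in this study". Counts could well have recovered in some patients. This stands: a reader might infer that the trial will lose more than half its information, and the documents do not support that.

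A second objection is to raw-count ANCOVA as a replacement. Its interval under-covers in exactly the case the primary objective hopes for, a clear difference between doses, while the t-test stays close to nominal. This also stands. It rules out substituting raw-count ANCOVA for the t-test and makes the log-scale model more than an option.

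Third, adjustment may already be planned. Section 9.6 defers to the SAP, and Section 10.3 says that statistical abbreviations were added because of the revised statistics section. One cannot infer that ANCOVA has been ruled out; Section 9 simply does not mention it.

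Fourth, Section 9.6 can be read as giving the 95% CI to the summarized change in each arm and only a test to the difference. That is a fair reading, and a reason to state the interval for the difference explicitly.

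Finally, the study is exploratory. That lowers the stakes, but it does not remove a cheap gain in precision.

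**Conclusion.** The concern holds as a conditional loss of precision. With 20 evaluable patients, the unadjusted comparison of change keeps less than half the information of a baseline-adjusted one whenever k is below about 0.69, for any correlation. The comparator is ANCOVA with a common slope and a roughly linear relation to baseline. The threshold is sufficient, not necessary: at ρ = 0.3, for example, half is already lost at k = 0.76. Whether k will fall that low cannot be judged from the protocol.

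A reader might go further and call the t-test wrong or biased. It is neither: its Type I error was close to nominal in the normal simulations and not materially inflated in the skewed ones. The change is worth making but not essential, and confidence is medium because k is unknown.

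**What to change.** In Section 9.6 and the SAP, for Trm number:

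- Add an ANCOVA of the Week 52 count on arm and baseline lesional count, using the data after Section 9.4 handling. Report the adjusted arm difference with its 95% CI next to the planned t-test on change. ANCOVA of Week 52 and ANCOVA of change give the same difference and interval, so the endpoint is kept.
- Also specify, not as an option, an ANCOVA of log Week 52 on arm and log baseline, with a rule for zero counts. It estimates a ratio between arms, so it complements the difference in counts.
- Fix the scale before any between-arm Trm data are analysed.
- If the SAP already specifies ANCOVA, align Section 9.6 with it.

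No new data are needed, and the model uses one degree of freedom. If counts have recovered, the adjusted interval is wider by the amounts shown in the working. A protocol amendment needs IRB approval (Statement of Compliance). Section 6.3 unblinds investigators, staff and patients one patient at a time at Week 52, so the change should be dated and documented, with a statement of which Trm data had been seen by then.

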The protocol, Informed consent form(s), recruitment materials, and all participant materials will be submitted to the IRB for review and approval. Approval of both the protocol and the consent form must be obtained before any participant is enrolled. Any amendment to the protocol will require review and approval by the IRB before the changes are implemented to the study. All changes to the consent form will be IRB approved; a determination will be made regarding whether a new consent needs to be obtained from participants who provided consent, using a previously approved consent form.

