1. PROTOCOL SUMMARY

1.1. SYNOPSIS

Title: “Decreasing resident memory T cells while increasing clinical durability: higher induction doses of risankizumab for moderate-to-severe plaque psoriasis (KNOCKOUT)”

Study Description: This is a pilot study that explores whether higher induction doses of risankizumab (2x and 4x standard induction doses) can more effectively target resident memory (Trm) cells within psoriatic lesions, and whether more profound knock-down of Trm is associated with higher levels of complete clearance (i.e., PASI 100) and for longer periods of time.

Objectives: **Primary Objective:** to determine whether the reduction in the number and/or effector function of epidermal CD8+CD103+ Trm cells at Week 52 (compared to baseline numbers) in psoriasis patients treated with 4X standard induction doses of risankizumab (600 mg at Weeks 0, 4, and 16) is greater when compared to psoriasis patients treated with 2X standard induction doses of risankizumab (300 mg at Weeks 0, 4, and 16).

Secondary Objectives:

- 1) to compare the percentage of patients with PASI 100 (complete clearance) at Weeks 28, 40, 52 and 100 in patients receiving 4X standard induction doses of risankizumab vs. those receiving 2X standard induction doses of risankizumab and
- 2) to compare safety events over 100 weeks in patients receiving 4X standard induction doses of risankizumab vs. those receiving 2X standard induction doses of risankizumab

[figure not shown]

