6.1.2. DOSING AND ADMINISTRATION

Twenty patients with moderate to severe plaque psoriasis will be randomized in a 1:1 manner to receive either risankizumab 600 mg (4X dosing) or 300 mg (2X dosing), SC, at Weeks 0, 4, and 16. All patients will receive four SC injections at Weeks 0, 4, and 16 (into right arm, left arm, right thigh, left thigh) by an unblinded pharmacist. For patients randomized into the highest induction dose arm, each shot will contain 150 mg of risankizumab; for patients randomized into the 2X induction dose arm, two shots will contain 150 mg of risankizumab each and 2 shots will contain placebo (sterile saline).

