5. **CyTOF Imaging:** Formalin-fixed, paraffin-embedded tissue slides will be heated for 2 hours at 60°C, deparaffinized, and rehydrated. Slides will be placed in pH 9 Tris/EDTA antigen retrieval buffer and heated at 96°C for 30 minutes. After cooling, slides will be blocked in 3% BSA, and stained with a cocktail of metal-tagged antibodies overnight at 4 °C including CD45, E-Cadherin, CD4, CD8, collagen, and pan-actin, and TRM markers CD27 (Fluidigm #3171024D), CD127 (Fluidigm # 3168026D). These have already been optimized in a panel for staining at our labs. For staining for CD69, CD103, CD49a, and circulating memory markers: CD62L, CCR7, we will optimize those using Imaging Mass Cytometry Staining Protocol for FFPE sections. The stained tissue is ablated, and raw data acquired on the Hyperion Imaging System (Fluidigm).
6. **Imaging CyTOF Data Analysis:** Multiplexed imaging CyTOF data will be pre-processed using commercial acquisition software (Fluidigm) and converted to .TIFF images. These images will be segmented into individual cells using CellProfiler v3.1.8 for single-cell analysis. The t-SNE dimensionality reduction algorithm and the Phenograph unsupervised clustering algorithm will be performed on TRM markers (CD4, CD8, CD69, CD103, CD49a, CD62L, CCR7) using HistoCAT v1.75 software. For t-SNE and PhenoGraph, the data will be normalized to the 99th percentile. The Heatmap will be generated to show z-scored mean marker expression of each cluster. P values will be computed using 2-tailed Student's t tests assuming homoscedasticity.

Remaining tissue samples will be stored at the University of Michigan laboratory until the end of trial or until arrangement for shipping to AbbVie is made. Patient ICF will include language for future use of remaining tissue samples by AbbVie in additional research.

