9. STATISTICAL CONSIDERATIONS

9.1. STATISTICAL HYPOTHESES

The study is exploratory in nature and is not statistically powered to detect differences between the treatment arms. All analyses will be descriptive with the goal of developing hypothesis-generating data. The statistical analyses will be performed by AbbVie data and statistical sciences (DSS). Complete and specific details of the statistical analysis will be described and fully documented in the Statistical Analysis Plan (SAP). The statistical analyses will be performed using SAS (SAS Institute Inc., Cary, North Carolina, USA).

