9.7. METHODS FOR ANALYSIS OF SECONDARY OUTCOMES

For binary endpoints, after handling of intercurrent events in Section 9.4, the proportion will be summarized with percentage, 95% confidence interval, and compared between the two treatment arms with Fisher's exact test.

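### Section 9.6 names no two-sample rank test for the primary outcome; its only non-parametric example, the Wilcoxon signed-rank test, cannot compare two independent arms

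*Combined protocol and SAP*

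**What the plan says.** The primary objective (synopsis and section 3) is a contrast between arms: whether the Week 52 reduction in Trm cells at 4X "is greater when compared to psoriasis patients treated with 2X standard induction doses of risankizumab". Section 6.1.2 randomises twenty patients 1:1 to the two dose groups, so the arms are independent, at about 10 patients each, with no pairing or crossover.

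Section 9.6 summarises change from baseline with mean, SD and 95% confidence interval, and has it "compared between the two treatment arms with t-test". The next sentence reads: "Additional analysis with non-parametric test (e.g., Wilcoxon signed-rank test) will be performed, as appropriate". Further detail is left to the SAP.

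Only two other group tests are named. For the imaging data, section 8.1 says "P values will be computed using 2-tailed Student's t tests assuming homoscedasticity". For binary endpoints, section 9.7 has proportions "compared between the two treatment arms with Fisher's exact test". Section 9.1 sets the status of all of this: "All analyses will be descriptive with the goal of developing hypothesis-generating data".

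**The concern.** The non-parametric sentence follows directly after the between-arm t-test and reads as a robustness check on it, but it does not state its purpose. There are two readings, and each leaves a gap.

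- **Between-arm check intended.** The named test is the wrong one. The signed-rank test needs one sample of differences or matched pairs, and patients in two parallel arms are not matched.
- **Within-arm check intended.** The test is valid, because each patient has a Week 0 and a Week 52 lesional biopsy. The 4X versus 2X question then has no rank-based analysis.

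With about 10 patients per arm, one or two extreme changes can drive a t-test, so a rank-based check of the same contrast is useful here. A programmer who follows the example literally would produce one signed-rank p-value per arm. A table showing significance in one arm and not in the other invites the reader to infer a dose effect that has not been tested.

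**Working it through.** The plan gives no alpha, effect size, SD or power for this outcome, so there is no stated figure to reproduce. The check has a part that needs no effect-size assumption and an illustration that does.

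**Inputs.** From the documents: 20 patients, 1:1, hence 10 per arm if every patient has both biopsies. Assumed: two-sided 0.05 and, for the illustration only, normally distributed changes with SD 1.

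**1. Exact p-values when every patient improves**

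Signed-rank, n = 10, all changes negative: p = 2/2^10 = 2/1024 = 0.00195. This value is the same in each arm, whatever the other arm does.

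Rank-sum, 10 versus 10:

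- *Complete separation* (every 4X fall exceeds every 2X fall): p = 2/C(20,10) = 2/184,756 = 0.0000108.
- *Interleaved* (falls of 1, 3, ..., 19 in one arm and 2, 4, ..., 20 in the other): U = 0 + 1 + ... + 9 = 45, against a null mean of 10 × 10/2 = 50. Exact p = 0.739.

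The signed-rank result is therefore 0.002 and 0.002 in both cases. It cannot tell the largest possible separation of the arms from almost none.

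**2. Illustration: identical arms, no dose effect**

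Both arms have the same true fall, in SD units. Let p be the within-arm signed-rank rejection rate. The arms are independent, so P(exactly one arm significant) = 2p(1 − p). At zero fall, p is the exact size of the test, 0.0488, and 2 × 0.0488 × 0.9512 = 0.093. At 0.8 SD, 2 × 0.597 × 0.403 = 0.481. Rates for non-zero falls come from simulation with exact tests.

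| Common fall (SD) | Signed-rank rejects, each arm | Exactly one arm significant | Rank-sum rejects |
|---|---|---|---|
| 0 | 5% | 9% | 4% |
| 0.2 | 9% | 16% | 4% |
| 0.5 | 28% | 41% | 4% |
| 0.8 | 60% | 48% | 4% |
| 1.0 | 79% | 34% | 4% |
| 1.43 | 97% | 5% | 4% |

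With 8 versus 10 evaluable patients, exactly one arm is significant in 8, 36, 44 and 13% for falls of 0, 0.5, 1.0 and 1.43 SD. Rank-sum again stays at 4%.

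**3. Forcing the signed-rank test across arms**

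Pairing 4X patients with 2X patients arbitrarily gives no unique answer. In one simulated 10 versus 10 data set, 2,000 random pairings gave signed-rank p-values from 0.002 to 0.23. The rank-sum p-value for the same data was 0.019.

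**4. Price of the rank-sum test**

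At an assumed true difference of 1 SD between arms, 10 per arm and normal data, power is about 51% for the exact rank-sum test and 56% for the t-test.

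**The case against.** The strongest reply is that section 9.6 fixes nothing. The test is offered as an example, to be used as appropriate, with details left to the SAP. A rank-sum test is not excluded, and a fuller SAP may name one. A valid reading also exists: the data are paired within patient, and the sentence does not say that the non-parametric analysis is between arms. On that reading nothing is wrong, the t-test already answers the between-arm question, and nothing in the plan requires a second test of it. The one-arm-significant rates describe a misreading that the plan does not propose, and they depend heavily on an assumed fall. Finally, the study is exploratory, unpowered and descriptive.

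Most of this stands as a limit on weight. The t-test is untouched, no endpoint or analysis set changes, and the simulated rates are illustrations only. It does not remove the point. The only example given for the primary outcome does not fit the primary contrast, and the within-arm reading still leaves that contrast without a rank test. The exact p-values in step 1 rest on no assumed effect. Deferral to the SAP makes the correction easy; it does not make the example right.

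**Conclusion.** Wrong as written, with limited consequence. The named test cannot compare the two randomised arms, and no two-sample rank test appears in the supplied text. A signed-rank p-value of 0.002 in each arm is compatible with a rank-sum p-value anywhere from 0.00001 to at least 0.74. If the example were run arm by arm and the results contrasted, a spurious one-arm-only pattern would arise in roughly 5 to 48% of trials with no dose effect. That range assumes normal changes, 10 per arm, two-sided 0.05 and common falls of 0 to 1.43 SD, none of which the documents give except the arm size. The point concerns a supportive analysis in an exploratory study and should be fixed before the SAP is final. Confidence is high on the statistical fact; which reading the sponsor intended is not known.

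**What to change.** In the SAP, name the exact two-sided Wilcoxon rank-sum (Mann-Whitney) test on Week 52 change from baseline, 4X versus 2X, as the non-parametric between-arm analysis, and settle this before results can influence the choice. If the signed-rank test is kept, label it as describing within-arm change from baseline only and as no evidence of a difference between doses. Optionally, report the Hodges-Lehmann between-arm shift with a 95% confidence interval.

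The cost is one line in the SAP, with no new data, patients or visits. The matching wording in section 9.6 needs IRB approval under the Statement of Compliance and can wait for the next amendment.
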